### 1.0 Summary of research

**Design:** A mixed methods study to develop and test the feasibility of an intervention to improve return to work in NHS staff who go on sick leave with a CMHD.

Method: The study is divided into 2 phases:

- Phase 1 aims to test the feasibility and acceptability of the intervention in the NHS
  and to assess for contamination if the main trial were to be a randomised controlled
  trial at departmental level.
- Phase 2 finalises the manualised intervention and makes recommendations on the best study design for a future trial.

A significant amount of preparatory work was completed prior to phase 1/2 and a full description of this work can be found in the appendix.

We will carry out phase 1 in six OH departments (study centres). At three study centres, study participants will be assigned either to see an OH nurse who has been trained as a case-manager and will receive the intervention or to see an OH nurse who has not been trained as a case-manager and will receive CAU. At two centres, participants will receive CAU only and at one centre, participants will be assigned an OH nurse who has been trained as a case-manager. This design allows us to test for feasibility of the intervention in a NHS setting and to assess the risk of contamination if a cluster RCT were undertaken.

**Setting:** Six OH departments delivering services to different types of NHS Trusts. **Target population:** NHS staff who have recently been issued with a fit note which includes a CMHD.

**Inclusion criteria:** Staff with a CMHD with or without an associated physical disorder, who have been off sick for more than 7 days and fewer than 90 days. Employee must be off sick when referral made to OH and when completing baseline questionnaire.

**Exclusion criteria:** Staff with a psychotic disorder, bipolar disorder, substance misuse disorder or dementia. Staff under investigation for misconduct or in the process of formal disciplinary action.

**Health technologies being assessed:** Standardised case management delivered by OH nurses following training. The intervention is likely to include identifying barriers to RTW, problem solving, peer-support networking, work-focused CBT, optimisation of clinical treatment and goal setting. An agreed written RTW plan with workplace adjustments, based on discussion between participants and their manager and shared with the participants' healthcare professionals. Regular timed reviews.

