# 2.4.2 Occupational outcomes

We will measure full RTW (defined for this study as working the same days or hours per week as before sickness absence in an identical or equivalent role for at least four weeks) and partial RTW (defined as working any number of hours in any role) through the ESR and self-completion questionnaires. A study examining a multi-stakeholder perspective on the definition of RTW after sickness absence due to CMHD found that definitions of RTW based on working days and hours may not accurately reflect the priorities of all stakeholders (Hees et al. 2012). Therefore we will select the most appropriate questions and discuss with our public and patient involvement (PPI) representatives.

A number of instruments have been developed to measure presenteeism, and whilst all have pros and cons we will measure workability by using the Work Ability Index (Ilmarinen, Tuomi 1992). This self-report questionnaire has been used in other sickness absence studies and will allow us to explore the effect of physical co-morbidity on work ability (Ahlstrom et al. 2010) and has shown to be a reliable instrument in this context. We will also use the Work and Social Adjustment Scale (Mundt et al. 2002) as a measure of global functioning. Using both these measures of occupational outcomes will allow us to compare the results from the measures and select which one would be the optimum measure in the full trial.

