We will collect the same data on all participants and participating centres. Data from all groups will be used to answer questions about rates of recruitment and follow-up, and the acceptability and performance of methods to assess possible outcome measures. Data from Group A and Group D will provide information about the acceptability and costs of the intervention, and rates of adherence to the intervention. Data from Groups B and C will provide information about the distribution of possible outcome measures in the absence of the intervention (which would help in power calculations for a subsequent trial). Comparison of the management of participants in Groups B and C will give an indication of potential for major "contamination". The follow-up period will be six months from recruitment. Outcomes will be assessed using a mix of qualitative and quantitative methods.

Target population: NHS staff who have recently commenced sick leave because of CMHD

**Inclusion criteria:** Staff with CMHD with or without an associated physical disorder who have been off sick for a period of more than 7 days (i.e. on receipt of fit note) and less than 90

days. Staff will be screened for eligibility for entry into the study either at the time of referral to OH or during their 1st OH appointment.

**Exclusion criteria:** Staff with a psychotic disorder, bipolar disorder, substance abuse or dementia. Staff under formal investigation for misconduct or in the formal process of disciplinary action (as this may be an effect modifier).

Six OH departments have been chosen from those confirming that they wished to participate in the feasibility study in response to the questionnaire sent to the current SCIN study centres plus one ambulance trust. We have selected NHS OH departments representative of the range of NHS Trusts in the UK, providing OH services to a mixture of acute, mental health and ambulance trusts. All trusts included have electronic OH data capture systems, do not currently have early (<8 day) intervention for sickness absence or case-management in use and employ more than two OH nurses who advise on RTW in workers with CMHD.

We have allocated the participating trusts to care as usual or mixed intervention/ care as usual centres / intervention centre based on sampling groups with the aim of achieving broad comparability between the types of trust.

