# 6.4 Data collection and follow up 6.4.1 Quantitative data

Data on sickness absence for CMHD will be collected for six months after the participant enters the study from S10 on the participating centre's ESR and by self-report questionnaire. Study participants will be given a self-administered baseline questionnaire to complete at the time of entry to the study (t=0). They will be sent a follow-up self-administered intermediate questionnaire at three months (T=3) and a final follow-up self-administered questionnaire at six months (t=6) after entry to the study. Note, all participants will complete the same baseline and intermediate questionnaires. Responses provided in the intermediate questionnaire will than determine which version of the final questionnaire will be administered i.e. final questionnaire (version 1) will be administered to those employees who are back at work in any capacity for more than four weeks at the three month time point (T=3); final questionnaire (version 2) will be administered to those who are still off on sick leave at T=3months due to their mental health condition (including those who have not returned to sustained work) or those who did not return the intermediate questionnaire.

Participants will be invited to complete paper-based questionnaires. This will be returned to the central research team using business reply envelopes. A series of reminders will be used to encourage return of the study questionnaires for non-responders. The reminders will include, one email reminder, one telephone reminder and finally a replacement questionnaire will be sent to the participants preferred postal address. To allow to send participants 3 and 6 months questionnaires (and reminders if needed), we will collect contact details from participants (name, surname, mobile phone, email address, home postal address). Contact details will be collected together with the baseline questionnaire.

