We will collect information about: rates of recruitment; reasons for non-participation; baseline characteristics of those eligible for inclusion; adherence to the intervention in those allocated to receive it and the management of those who are not; and rates of successful follow-up. Additionally, we will collect data on the distribution of possible outcome measures, including, reduction in anxiety/ depression, health-related quality of life, change in antidepressant use and RTW during the six month study period. Full and partial return to work will be measured by total days of sickness absence before return to work and self-reported number of hours worked. We will collect information about participants' referral to and uptake of improving access to psychological therapies (IAPT) services and the Government's Fit for Work Service We will record any protocol violations, reasons for not completing the intervention and any adverse events.

At the sponsor site (Guy's and St Thomas NHS Foundation), we will conduct further exploratory work to better understand the factors impacting on the identification and referral of employees who are on sick leave with a common mental health disorder. Where appropriate and with relevant permissions, this may include reviewing information on existing management referrals. These insights will be pooled with information obtained from the focus group interviews.

Costs of delivering the package of interventions including OH nurse time, participant and manager time and cost of training OH nurses in case management.

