# 6.5.1 Quantitative

Rates of recruitment will be calculated from the numbers of eligible participants and of those who agree to participate in the study. Characteristics of eligible participants will be recorded at baseline and will be summarised through means, medians, standard deviations, and interquartile ranges (IQRs). Characteristics will be compared between those who agree to participate in the feasibility study and those who do not. Outcome variables, including anxiety/depression score, health related quality of life score, use of antidepressants, will be summarised separately for baseline and follow-up using means and standard deviations if they are normally distributed, or through medians and IQRs otherwise. Number of days before returning to normal working hours will be summarised by medians and IQRs. For each possible outcome measure, the prevalence of missing data will be quantified. We will calculate the proportion of participants who complete the intervention, and the proportion of completed data sets.

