### 11.0a Governance and legal compliance

) We will apply for Health Research Authority approval study. . We will apply for Research and Development (R&D) approval via the new Health Research Authority's system and R and D approval from each centre via the site specific forms.

Although 49 of the participants will not receive the intervention, they will receive care as usual for their Trust. The participating centre will benefit from help with standardising the data collection of their sickness absence. Our experience from the SCIN trial and other studies in NHS staff has been that NHS staff are keen to participate in research studies which aim to improve the health of NHS staff, provided that questionnaires do not take too long to complete. NHS staff understand the importance of collecting data from participants who may not receive the intervention. Our experience is that NHS staff embrace the concept that 'research is everyone's business.'

Participants who receive the intervention, but have not returned to work after six months, will, at the discretion of the participating centre, continue to receive the intervention until they return to work. Our data on RTW times for NHS staff who go on sick leave with CMHD suggests that most of the participants are likely to have RTW by six months after being recruited into the study.

Approval for the study will be obtained in advance from the management and staff representatives at the participating trusts. Informed consent will be sought from all staff participants before entry into the study. If first occupational health appointment occurs face to face, OH nurse will take written informed consent at the commencement of the first appointment; if first OH appointment occurs by telephone, OH nurse will take informed consent at the commencement of the first telephone consultation and verbal consent will be documented on the consent form..Data collection will be organised such that names and contact details of individuals who take part in the study are held separately from other personal information, which will be identified only by a serial number. No information will be published in a form that could lead to the identification of individuals.

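### Section 6.5.1 gives time to normal working hours a plain median and IQR, with no stated time zero, no rule for people not back at six months, and an event wording that omits the four-week condition

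*Protocol*

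**What the plan says.** The planned summary, in section 6.5.1, is one sentence: "Number of days before returning to normal working hours will be summarised by medians and IQRs". The only accompanying provision for absent values is that the amount of missing data will be quantified for each outcome.

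Five other places bear on it.

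- **End of observation.** Section 6.1: "The follow-up period will be six months from recruitment". Section 6.4.1: "Data on sickness absence for CMHD will be collected for six months after the participant enters the study".
- **Non-return is foreseen.** Section 11.0a provides for "Participants who receive the intervention, but have not returned to work after six months" and says only that "most of the participants are likely to have RTW by six months after being recruited into the study". Section 6.3 also allows for people still on sick leave when the study finishes.
- **Entry.** Section 1.0 admits staff "who have been off sick for more than 7 days and fewer than 90 days".
- **Measurement.** Section 6.4.1 says that full and partial return will be "measured by total days of sickness absence before return to work", together with self-reported hours.
- **Event.** Section 2.4.2 defines full return as "working the same days or hours per week as before sickness absence in an identical or equivalent role for at least four weeks".

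Section 2.3 describes the team's own trust absence data with a Kaplan-Meier curve. Sections 6.1 and 7.0 say that outcome distributions without the intervention will help inform power calculations for a later trial.

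**The concern.** Days until return is a time-to-event variable with a fixed end of observation. Someone still off at six months has no number of days before returning, only a lower bound. A plain median and IQR needs a rule for such people, and the sentence gives none. The easiest way to carry it out is to compute it on those with a value, and that shortens every quartile.

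The clock is also open. The measurement wording in 6.4.1 suggests counting from the start of absence, while data collection runs from study entry. For one person the two can differ by up to 89 days.

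The event is open too. A first day at normal hours and a first day of four sustained weeks in the same or an equivalent role are different dates, and a return in the last 28 days of follow-up cannot be shown to be sustained.

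At stake is the usefulness of this distribution for planning the definitive trial. The participation-rate sample size is not affected.

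**Working it through.** **The plan's own figure.** None is given for time to return. The one computed design figure, 60 participants for an 80% participation rate to within 10 points, reproduces closely: 1.96 × √(0.8 × 0.2 / 60) = 10.1 points. It has no bearing here.

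**Effect of leaving out non-returners, without any curve.** If a fraction f is not back and is omitted, the reported median is the 50(1 − f)th percentile of those enrolled, and the reported upper quartile is the 75(1 − f)th.

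- f = 5%: 47.5th and 71st percentiles.
- f = 10%: 45th and 67.5th.
- f = 20%: 40th and 60th.

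The protocol gives no six-month value for f. Section 2.1 says only that over 75% eventually return.

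**Size in days.** Inputs from section 2.3 (Figure 2, mental-illness absences): 21.23% last under 7 days, so S(7) = 0.7877; 47.91% last over 28 days, so S(28) = 0.4791.

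- Weibull: shape = ln[ln S(28) / ln S(7)] / ln 4 = ln(0.7358 / 0.2386) / 1.386 = 0.812; scale = 28 / 0.7358^(1/0.812) = 40.8 days.
- Lognormal through the same points: μ = 3.247, σ = 1.629.

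Assumptions: entry uniform over days 8–28 or 8–89 among those still absent; observation ends 183 days after entry; no other losses. Spells were simulated, and quartiles of time from entry were compared between returners only and everyone enrolled.

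| Curve, entry days | Not back | Median: returners v all | Upper quartile: returners v all |
|---|---|---|---|
| Weibull, 8–28 | 4.3% | 31.0 v 33.2 | 64.7 v 71.7 |
| Weibull, 8–89 | 4.9% | 33.6 v 36.2 | 68.4 v 76.8 |
| Lognormal, 8–28 | 17.3% | 30.6 v 43.3 | 69.6 v 122.2 |
| Lognormal, 8–89 | 23.1% | 37.9 v 60.4 | 81.1 v 167.3 |

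**Which curve is more credible.** Figure 2 also gives shares of days absent: 1.10%, 9.28% and 89.62% for spells under 7, 7–28 and over 28 days. If these reflect whole spell lengths, the Weibull implies 1.4%, 10.9% and 87.7%, and the lognormal 0.8%, 5.0% and 94.3%. The Weibull is closer. A generalised gamma made to match S(7), S(28) and the over-28-day share lies between: 8.5% to 10% not back, medians 31 v 36 (entry days 8–30) or 36 v 43 (8–89), upper quartiles 68 v 85 or 75 v 97.

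**Four-week condition.** In these simulations 2.2% to 3.6% of those enrolled return in the last 28 days of follow-up. Of 77 participants that is 77 × 0.022 = 1.7 to 77 × 0.036 = 2.8, so about two or three people.

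**The case against.** The strongest reply is that the protocol nowhere says non-returners are dropped. A reader might infer from 6.5.1 that the summary can describe returners only; the text does not support that. Medians and quartiles depend on ranks. Timed from entry, with everyone followed for six months and non-returners ranked last, the median is valid if fewer than 50% are not back, and the full IQR if fewer than 25%. Every scenario above meets both conditions. This stands, and it makes the bias conditional. But the protocol states neither the ranking nor the clock, and ranking last does not deal with people lost before six months.

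A reader might also infer that a median counted from the start of absence is too long, since it exceeds the median of all spells over a week. That comparison is misplaced: the trial envisaged in 6.1 recruits the same 8-to-89-day population, so for planning it the enrolled distribution is the relevant one. What survives is that time zero is not stated.

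Nor does 6.5.1 cancel the four-week rule. Section 2.4.2 defines full return for the whole study, and 6.5.1 need not repeat it. Still, the two wordings describe different events, and nothing says which one dates the return.

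Finally, precision is low. Groups B and C total 21 + 28 = 49 people. Under the generalised gamma with entry at days 8–30, sampling error alone would spread a median over roughly 22 to 57 days, well beyond a 5-day bias. The version log (v1.3) also records that the definitive trial's primary outcome became hours until return. Both points lower the severity. Neither supplies the missing rule, and hours until return has no value for non-returners either.

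**Conclusion.** The point holds as a defect in a summary that the protocol itself fixes, not as a complaint about detail left to an analysis plan. A plain median and IQR is prescribed for a variable that some participants will not have, with the clock unstated and the event worded differently from its definition.

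If non-returners are left out, the best-supported two-point curve puts the shortfall at 2 to 3 days in the median and 7 to 8 days in the upper quartile, with about 5% not back. The shortfall is larger if the tail is heavier. The lognormal extremes (38 v 60 days for the median, 81 v 167 for the upper quartile) should not be taken as the likely size, because that curve overstates the share of days in long spells. All of these figures extrapolate from day 28 to well beyond six months and rest on the assumed entry patterns.

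Severity is moderate: the outcome is descriptive, few people are affected, and the remedy is cheap.

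**What to change.** Replace the sentence in 6.5.1 with:

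*Time from study entry to the first day of full RTW (as defined in 2.4.2) will be summarised by Kaplan-Meier quartiles with 95% CIs, censoring at the end of follow-up, together with the proportion not back at six months. If any participants leave employment, a cumulative-incidence estimate treating this as a competing event will be reported.*

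The second sentence is needed because Kaplan-Meier does not itself treat leaving employment as a competing event.

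Three additions:

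- Report days of absence already accrued at entry as a separate baseline summary. Use delayed entry only if a secondary analysis runs from the first day of absence.
- State that returns in the last 28 days of follow-up (about 2% to 4% of participants under the assumptions above) cannot be confirmed as sustained from the planned data, and say how they are classed. A later staff-record extract may not settle this alone, because code S10 records absence while hours worked are self-reported.
- Use the same time origin and event wording in 2.4.2, 6.4.1 and 6.5.1.

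The cost is a short text change and slightly more analysis work. No new data collection is needed.

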# 6.5.2 Qualitative

Qualitative analysis of data from focus groups and interviews will involve thematic (i.e. content) analysis, including simple counting and inclusion of deviating accounts. The analysis will follow a six phase structured approach involving: (i) transcription of all interviews by a professional transcriber; (ii) familiarisation with text and creation of an initial list of emerging themes; (iii) coding of transcriptions uploaded to NVivo 8, a qualitative software package that allows data to be annotated as codes, and for the cross-referencing of codes; (iv) categorisation and interpretation through additional coding phases and development of

representative themes and theoretical concepts emerging from analytical induction and cross-checking with an additional researcher on the team; (v) identification of thematic frameworks in additional discussions with the team focused on further refinement through constant comparison within and between the codes to ensure that the framework reflects the data; and (vi) linking findings with existing or newly generated theoretical concepts and models to provide context and confirm the relevance and robustness of the key findings of the study.

### 6.5.3 Economic

The economic component of the study will assess the feasibility of conducting an economic evaluation of an adequately powered trial. In order to inform the design of an economic evaluation of a full trial, we will identify which services are commonly used so that these can be included in the Client Service Receipt Inventory. We will also assess the feasibility of obtaining economic data and the extent to which questionnaires are completed and return the required information.

### 6.6 Sample size

We calculated that with a sample size of 60 we will be able to estimate a participation rate of 80% to within a 95% confidence interval of +/- 10%. We have allowed for a maximum of 77 participants so we are confident that we will have a good precision around the participation, and completion rates. All the OH departments who have confirmed that they wish to take part would expect to see more than 20 workers who go on sick leave with CMHD in a six-month period. Therefore, we consider that it is feasible to recruit 14 participants at care as usual and mixed intervention/care as usual centre and 7 participants at the intervention only centre.

